6.10 Termination

A subject's participation will be terminated if one of the following occurs:

- a. Subject voluntarily withdraws
- b. Subject fails to comply with study procedures
- c. Decision in the best interest of the patient
- d. Patient is no longer eligible for care at the military HIV clinics
- e. Patient becomes pregnant or decides to become pregnant during the two-year study period

- f. The patient begins employment as a healthcare worker with direct patient contact

A subject who develops a rash or significant adverse event due to study medication will be discontinued from treatment but will be encouraged to continue to undergo follow up including study visits for completing questionnaires and swabs for MRSA colonization every 6 months (+/- 2 months) until study completion; the patient will not be randomized to one of the treatment arms if he/she is found to be positive again for MRSA colonization. The subject may be withdrawn from the study if it is felt by the clinical investigators that the subject is at an undue risk from further participation.

The subject will require a termination visit if withdrawn from the study. If a subject's participation in this study is terminated, they will be offered medical standard of care and a medical evaluation, to include clinical laboratory studies as needed. The investigator will complete the Completion/Discontinuation CRF.

VII. STATISTICAL ANALYSES

There are four primary questions to be answered to address this study's primary objective. These, and an analysis designed to answer the question, follow.

- (1) What is the hexachlorophene/mupirocin treatment effect to clear MRSA colonization compared to placebo? We will also examine if these decolonization procedures are effective at reducing MRSA infections and skin/soft tissue infections compared to placebo. We propose to pool the data at 6, 12, 18, and 24 months as if they were independent and conduct a chi-square or Fisher's exact test of contingency. These analyses will be conducted for colonization and infection separately. The proposed pooling of this study design assumes that there is no persistent or repeated-treatment effect and that there is no patient-to-patient difference in susceptibility. These effects will be investigated in the following questions.

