- (2) Is the treatment effect different for repeat administrations of hexachlorophene/mupirocin? The rate of MRSA positive versus negative for recolonization reoccurrence through the sequence 1 versus 2 versus 3 versus 4 treatments will be assessed by a test of trend.
- (3) Is there a persistent or repeated-treatment effect? The overall rates of MRSA recolonization at 6, 12, 18, and 24 months will be assessed by a test of trend.
- (4) Is there an individual propensity for susceptibility and what are the treatment differences between placebo and hexachlorophene/mupirocin in terms of length of time for being negative for MRSA colonization on repeated testing? A Kaplan-Meier long-rank test will be conducted on three groups: initially negative, initially positive treated with hexachlorophene/mupirocin, and initially positive treated with placebo, where survival is defined as not having acquired MRSA.

For the secondary objectives, part (a) will be assessments of the rates in which prevalence is defined as the number of patients colonized with MRSA at the beginning of

the study divided by the total population studied, and the incidence as the number of new infections per calendar time divided by the total population studied. For objective (b) examining for predictors of MRSA, we will create a multivariate logistic regression model and use a backward stepwise approach. For part (c), to evaluate if there is a significant change in the CD4 count and/or viral load pre- versus during a MRSA infection we will utilize a 1-way ANOVA. We will also compare pre-MRSA infection with after MRSA resolution as well as the counts during the infection with those after resolution. Finally, objective (d) will be a descriptive analysis of the molecular and microbiologic characteristics of the isolates. The main statistical data from the retrospective chart review study of HIV patients at NMCSD will be presented by descriptive analyses. We will compare demographics and HIV clinical data between those with and without MRSA using rank sum tests and Fisher's exact tests depending on the variable characteristics (categorical or continuous). A multivariate logistic regression model for predictors of MRSA will then be developed using a backward stepwise approach using Stata software.

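### The three-group log-rank test in question (4) cannot separate patient-to-patient susceptibility from persisting carriage, relapse or a drug effect

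*Combined protocol and SAP*

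**What the plan says.** Section VII lists four primary questions. Question (1) pools the 6-, 12-, 18- and 24-month results in a chi-square or Fisher's exact test, and notes that this pooling "assumes that there is no persistent or repeated-treatment effect and that there is no patient-to-patient difference in susceptibility". It continues: "These effects will be investigated in the following questions". Questions (2) and (3) use trend tests for repeat and persistent treatment effects. Susceptibility is taken up only in question (4), which asks two things at once: "Is there an individual propensity for susceptibility and what are the treatment differences between placebo and hexachlorophene/mupirocin". The treatment difference is to be measured as "length of time for being negative for MRSA colonization on repeated testing".

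One method serves both halves: "A Kaplan-Meier long-rank test will be conducted on three groups: initially negative, initially positive treated with hexachlorophene/mupirocin, and initially positive treated with placebo". The event is fixed only by a short closing clause: "where survival is defined as not having acquired MRSA". The section gives no time origin for patients who are already positive, no pairwise contrast and no patient-level term.

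**The concern.** The null of a three-group log-rank test is that the three curves coincide. The groups are formed by carriage at the start and by treatment, so they can differ for reasons unrelated to how susceptible each patient is: carriage may last from one visit to the next, a cleared carrier may relapse, and the drug may work. Differences between patients within a group do not enter the test, and at 10% carriage about 90% of patients sit in one group, the initially negative.

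This is the plan's only stated check on the susceptibility assumption behind the pooled primary test. A small p-value could be read as showing that some patients are inherently prone to MRSA and that pooling fails, when lasting carriage alone would produce it. A large p-value would not establish homogeneity. Because the time origin is open, the analyst could also choose, after seeing the data, between a test that is almost sure to reject and one that may be near nominal.

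**Working it through.** **Inputs from the documents.** Section VII: 550 enrolled, 10% colonized, 1:1 allocation, 85% of placebo and 7%, 23% or 39% of treated carriers still colonized, alpha 0.05. Section 6.3: swabs at months 6, 12, 18 and 24.

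**Assumed input.** The documents give no acquisition rate. Let q be the probability of acquisition per six months, the same for every patient, ranging from 1.7% to 10%. The lower end keeps prevalence at 10% with 85% persistence: 0.10 = 0.10 × 0.85 + 0.90 × q, so q = 0.015/0.90 = 1.67%.

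**Step 1: the plan's own table.** No size or power is given for question (4), so the check is on the table that supplies the rates. For two proportions, two-sided 0.05, power 0.80:

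n = [1.96√(2p̄(1−p̄)) + 0.842√(p₁(1−p₁)+p₂(1−p₂))]² / (p₁−p₂)²

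With continuity correction, n′ = (n/4)[1+√(1+4/(n|p₁−p₂|))]². For 85% v 23%, n = 8.86 and n′ = 11.87, so 12 carriers per arm. The three rows give 8, 12 and 21; divided by 0.10 these are 80, 120 and 210 per group, as stated. The rates are therefore read correctly.

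**Step 2: groups.** 550 × 0.10 = 55 carriers (27 treated, 28 placebo), leaving 495 initially negative.

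**Step 3: clock from baseline, event = first positive follow-up swab.** All patients share the same q (1,000 runs per cell). At 85% v 7%, 23% or 39%, the three-group test rejects in 100% of runs for q = 2%, 5% and 10%. With no drug effect (85% v 85%) it still rejects in 100%. With weaker persistence, equal in both arms, rejection is:

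| Persistence | q = 2% | q = 5% | q = 10% |
|---|---|---|---|
| equal to q | 5% | 6% | 5% |
| 15% | 78% | 36% | 13% |
| 30% | 99% | 94% | 65% |
| 50% | 100% | 100% | 99% |

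The two-group comparison of treated with placebo behaves as it should on this clock: 4.9-5.3% rejection at 85% v 85%, and 87.5-100% at the plan's rates.

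**Step 4: clock from the first negative swab.** Only cleared carriers enter: 27 × 0.77 ≈ 21 treated and 28 × 0.15 ≈ 4 placebo. With no relapse and no lasting drug effect, rejection is 4.9%, 4.7% and 5.7% for q = 2%, 5% and 10% (4,000 runs); other set-ups gave up to 12%.

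Section VII cites 93% cleared and 61% still clear at day 90. If both are shares of all treated patients, relapse among those cleared is 1 − 0.61/0.93 = 34%. With 450 initially negative, 23 cleared treated and 4 cleared placebo patients, and relapse in the first interval (500 runs per cell):

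| Relapse | q = 1.67% | q = 5% | q = 10% |
|---|---|---|---|
| 2% | 10% | 6% | 5% |
| 5% | 22% | 12% | 9% |
| 10% | 46% | 30% | 19% |
| 34% | 99% | 92% | 74% |

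Other set-ups, varying the number cleared, the timing of relapse and whether cleared placebo carriers relapse, widen the ranges to 19-52% at 10% relapse and 53-100% at 34%.

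**Step 5: other causes of rejection.** A lasting drug effect alone, halving acquisition, gives 10% (q = 5%) and 24% (q = 10%). Real differences in susceptibility, timed from the first negative swab at a mean q of 5%, give 23-99.8% depending on the assumed spread. The test therefore responds to susceptibility but is not specific to it.

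**Step 6: a possible replacement.** A Mantel-Haenszel test asks whether carriage before the previous swab predicts a positive swab now, stratified by visit, previous result and assignment. In identical patients without relapse it rejects in 4.5-4.7%. With a patient random effect of SD 1-1.5 on the logit scale its power is 23-87%. Relapse after a negative swab also triggers it in identical patients: at 10% relapse it rejects in 11-39% in one set-up and 38-57% in another, and at 34% in 76-100%.

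**The case against.** Three arguments limit the point.

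First, the 100% result needs carriers to be timed from baseline. The survival definition speaks of acquiring MRSA and the outcome of time spent negative, so a carrier who has never cleared has arguably acquired nothing. On that reading the clock starts at the first negative swab. This stands, but the plan does not say so, and on that clock the result still depends on relapse.

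Second, a reader might infer that the test will always report patient differences when none exist, or that any relapse at all inflates the error many times over. The documents do not support either. Without relapse or a lasting drug effect the first-negative clock is close to nominal, and inflation is graded: 5-10% rejection at 2% relapse. The 34% figure comes from residents of long-term care facilities carrying MSSA or MRSA, and may not carry over to these patients.

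Third, a reader might infer that the question (4) p-value decides whether pooling is valid. Section VII says only that the effects will be investigated. The plan also has a first-randomization-only analysis, a predictor regression and isolate typing. These limit the damage, but none is named as the check on susceptibility.

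Question (4) also asks for the treatment difference, and the treated-versus-placebo part of the comparison serves that purpose.

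**Conclusion.** The point holds as a mismatch between question and method. The three-group test cannot attribute a difference to susceptibility, so it cannot investigate the assumption that question (1) passes to it. On the baseline clock with 85% persistence on placebo, rejection in a homogeneous population is practically certain, against a nominal 5%. On the first-negative clock it runs from about 5-12% without relapse to about 53-100% at 34% relapse.

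These sizes rest on an assumed acquisition rate of 1.7-10% per six months and on scheduled visits only. Re-randomization, dropout and the four-weekly swabs of local carriers were not modeled. If those extra swabs are counted, carriers are tested more often than initially negative patients, which is a further reason for the curves to differ. The conclusion about what the test's null is does not depend on any of these assumptions.

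**What to change.** - **Limit the log-rank test.** Use it in question (4) only for treated versus placebo, with a stated time origin, and show the initially negative curve descriptively. A clock at the first negative swab would compare about 21 treated with 4 placebo patients selected after randomization; a clock at randomization keeps the randomized groups.
- **State what it does not show.** Say that its p-value is not evidence for or against patient-to-patient susceptibility or the pooling in question (1).
- **Add a patient-level analysis of the scheduled-visit swabs.** Use the history test of Step 6, or a logistic model with a patient random intercept, conditional on previous swab result and assignment. Report the odds ratio with its 95% CI.
- **Guard against relapse.** Repeat that analysis counting only new-strain positives, using the typing already planned in Section 6.3. Re-acquisition of the same type would be missed, so this version is conservative. Where typing cannot settle the matter, describe the result as susceptibility or relapse.

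The cost is SAP wording and one extra analysis with its sensitivity version, with no new data. Power for the propensity question is modest (23-87% in the runs above, before restricting to new strains) and should be stated.

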The trial will be a randomized, double-blinded study. Patients found to have a positive culture for MRSA colonization will be randomized in a 1:1 fashion to mupirocin (Bactroban®) nasal ointment plus hexachlorophene (pHisoHex®) soap for seven days or to a placebo nasal ointment (white petroleum) and a placebo body soap with no antimicrobial activity for seven days; since there is no standard therapy recommended in the guidelines for MRSA management for MRSA colonization, patients in the latter arm will receive placebos with no specific antimicrobial activity. In this design, we will ascertain if treatment for MRSA decolonization of this patient population is warranted or not. After completion of these topical medications, patients will complete a questionnaire to ascertain their adherence to these medications. Patients found to be colonized with MRSA and who reside locally (within driving distance) to the medical treatment facility will have repeat swabs (five swabs from sites listed above every four weeks (+/- 7 days) after any positive colonization cultures over the subsequent six month time period. These cultures will assist in determining if the decolonization medications were successful at eradicating the carriage of MRSA. Patients will receive one treatment course of either mupirocin (Bactroban®) nasal ointment plus hexachlorophene (pHisoHex®) soap for seven days or a placebo nasal ointment (white petroleum) and a placebo body soap with no antimicrobial activity for seven days. Patients who are initially found to be negative for MRSA on screening swabs will be re-evaluated in six months (+/- 2 months).

Patients who develop a soft tissue infection or any infection thought to be secondary to MRSA will be evaluated in the HIV clinic and will undergo wound cultures and repeated screening for MRSA colonization. CD4 counts and an HIV viral load will be obtained at the time of infection. Patient questionnaires and source documents will be completed for patients experiencing a soft tissue infection or MRSA infection.

Cultures (from colonization sampling and wound cultures) which are positive for MRSA or MSSA at the local medical treatment facilities laboratories will be sent to the San Antonio Military Medical Center (SAMMC) laboratory for confirmation of MRSA, antibiotic susceptibility testing, and molecular analysis.

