Patients who are colonized with MRSA and who reside locally to the medical treatment facility and are able to return to the clinic will have repeat swabs (five swabs from sites listed above) every month (+/- 7 days). A month will be specifically defined as 28 days. Those who have repeat positive colonization swabs during this initial 6 month follow-up period will be observed. This data will assess the efficacy of decolonization procedures on MRSA carriage rates. Patients who are not local to the clinic will not have these repeat swabs performed, but rather will be seen at the next scheduled 6 month study visit. Adherence to the study medications will be assessed at the next scheduled study visit by a patient questionnaire (refer to case report forms). Each time a patient has a positive isolate for MRSA or MSSA, this will be frozen and saved for molecular analysis to determine the most common molecular types colonizing HIV patients and to determine if patients acquire new strains or remain colonized with the same strain over time.

All study patients (both those initially found to be colonized with MRSA and those with negative colonization swabs) will be re-evaluated in six month intervals ($+/- 2$ months) until the end of the study. Patients found to be positive at these subsequent 6 month intervals, will be randomized again, treated and followed as described above. During the last study visit (at the 2-year time period), patients will have swabs, but not undergo randomization. Hence, every 6 months, patients positive during that visit for MRSA colonization will be re-randomized in a 1:1 double-blinded fashion to mupirocin (Bactroban®) nasal ointment twice daily for seven days plus hexachlorophene (pHisoHex®) washes with showering once daily for seven days or to a placebo nasal ointment (white petroleum) and a placebo body soap with no antimicrobial activity for seven days. Repeat randomization will occur every 6 months for those carrying MRSA. For example, some patients initially randomized to receive Bactroban® and pHisoHex®, may later be randomized to the placebo arm, and vice versa.

Begin at the top of diagram again every 6 months ($+/- 2$ months). If patient is found to be positive on swabs, they are re-randomized to one of the two treatment groups for every 6-month positive swab.

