APPENDIX D: SCHEDULE OF EVENTS

Event	Visit 1	Visit 2	Visit 3	Visit 4	Visit 5	Positive MRSA Colonization visit	MRSA Colonization Follow-up visit	MRSA/Soft Tissue Infection Visit	Additional / Unscheduled Visit
Study Month (Window: months)	0	6 (±2)	12 (±2)	18 (±2)	24 (±2)				
Informed Consent	X								
Inclusion/Exclusion Criteria	X								
Urine Pregnancy Test for women of childbearing age	X					X [#]		X [#]	
Enrollment	X								
Questionnaires including Medical History, Medications and MRSA Risk Factors	X	X	X	X	X	X		X	
Demographics	X								
MRSA Swabs for Colonization	X	X	X	X	X		X	X	
Randomization*						X		***	
Dispense Drug*						X		***	
AE Review***							X		X
Drug Accountability							X		
CD4 count/HIV Viral Load**								X	
Wound Culture and possibly blood cultures****								X	
Study Completion					X				

[#]Pregnancy test will only be performed at the MRSA colonization and infection visits among women who found to be colonized with MRSA; those with a positive pregnancy test will not receive the study medications and will be terminated from the study.

*Randomization into the mupirocin (Bactroban®) and hexachlorophene (pHisoHex®) soaps or to the placebo arm will only occur if a patient has a positive colonization swab for MRSA. Patients will be randomized in a 1:1 double-blinded fashion into these groups. Patients with colonization, regardless of the group assigned, will have repeat swabs for MRSA performed monthly (+/- 7 days) for six consecutive months. For patients with repeat positive MRSA colonization swabs on the 6-month visits, will be re-randomized during each of these events.

**AE review will occur among patients given mupirocin (Bactroban®) and hexachlorophene (pHisoHex®) or the placebo ointment and soap. AE's will be assessed that are temporally associated with study medications.

***Patients who are also found to have positive colonization swabs in addition to an infection will be randomized to one of the two treatment groups if this patient was not already randomized and the same procedures for a positive colonization visit will be followed.

****Patients presenting with a soft tissue infection will have wound cultures obtained if possible. Blood cultures also may be obtained at the primary treating physician's discretion

XVIII. ATTACHMENTS

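### Question (4)'s single three-group log-rank mixes two swab schedules, so its contrast of carriers with initially negative patients partly reflects more frequent looks (minor)

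*Combined protocol and SAP*

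**What the plan says.** Section VII opens its analysis list with "There are four primary questions to be answered" for the primary objective. Question (4) has two halves: whether individuals differ in propensity, and how the two arms differ in "length of time for being negative for MRSA colonization on repeated testing". One procedure serves both: "A Kaplan-Meier long-rank test will be conducted on three groups: initially negative, initially positive treated with hexachlorophene/mupirocin, and initially positive treated with placebo". No visit set, stratification or interval-censored method is named, and the time origin for carriers is not stated. Question (1), by contrast, names the 6, 12, 18 and 24 month data. Its pooling "assumes that there is no persistent or repeated-treatment effect and that there is no patient-to-patient difference in susceptibility", and section VII leaves those assumptions to the later questions.

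The swab schedules are set elsewhere:

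- Initially negative patients (section 5.1): "Patients who are initially found to be negative for MRSA on screening swabs will be re-evaluated in six months", with a ±2 month window.
- Local carriers (section 5.1): "Patients found to be colonized with MRSA and who reside locally (within driving distance) to the medical treatment facility will have repeat swabs", at 28-day intervals over the next six months.
- Non-local carriers (section 6.3): "Patients who are not local to the clinic will not have these repeat swabs performed"; they wait for the next 6-month visit.
- All groups (section 6.3): colonization swabs at an infection visit.

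Footnote * of Appendix D omits the local condition: "Patients with colonization, regardless of the group assigned, will have repeat swabs for MRSA performed monthly (+/- 7 days) for six consecutive months". Sections 5.1 and 6.3 are explicit, so they are taken as governing here.

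**The concern.** Acquisition is seen only when a swab is taken. A group swabbed more often shows positives earlier, and also shows short carriage spells that 6-monthly swabs miss. Local carriers have that extra opportunity; initially negative patients and non-local carriers do not. The log-rank nevertheless keeps everyone in one risk set between visits, as though all were equally observed.

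Two things are at stake. The propensity half of question (4) checks an assumption behind question (1)'s pooling, and more looks can make carriers seem more susceptible when they are not. In the arm comparison, non-local carriers who have not been swabbed count as negative alongside local carriers who have, which dilutes the arm difference.

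**Working it through.** **Inputs from the documents.** Section VII gives 500 patients followed and 10% colonized, so 500 × 0.10 = 50 carriers (25 per arm) and 450 initially negative. It assumes 85% of placebo and 7%, 23% or 39% of treated carriers remain colonized, and cites 61% still decolonized at day 90. Follow-up is 24 months.

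**Assumptions.** Local share L of 0.25, 0.5 or 0.8; mean carriage spell of 2 to 36 months; 10% of initially negative patients detected over 24 months. The documents give none of these. Section 5.2 says only that one site enrolls local patients exclusively, so L is above zero.

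**1. The plan's own figures.** No power is stated for question (4). The colonization sample sizes do reproduce. The two-proportion formula (two-sided 0.05, power 0.80, continuity correction) gives 8, 12 and 21 colonized patients per group. Divided by 0.10 these are 80, 120 and 210, as printed.

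**2. Plausible spell length.** The 85% persistence carries no day. With constant clearance, mean spell = −d / ln(0.85). For d = 28, 90 and 182 days this is 5.7, 18.2 and 36.8 months.

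**3. Carriers versus initially negative, no true difference.** Two-state carriage, 450 + 25 + 25 patients, all negative at time 0 with one acquisition rate, 20,000 trials per cell, 6-month visits at multiples of 182 days. Local carriers are also swabbed on days 28 to 168. Rejection of the three-group test at 0.05:

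| Mean spell (months) | 2 | 3 | 6 | 12 | 18 | 36 |
|---|---|---|---|---|---|---|
| L = 0.25 | 7.5% | 6.5% | 5.7% | 5.2% | 5.0% | 5.1% |
| L = 0.5 | 10.7% | 8.4% | 6.6% | 6.0% | 5.7% | 5.5% |
| L = 0.8 | 15.4% | 11.0% | 7.8% | 6.3% | 5.9% | 5.5% |
| Detection ratio by month 6, L = 0.5 | 1.76 | 1.49 | 1.23 | 1.11 | 1.07 | 1.04 |

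On the common visits only, rejection is 4.8–5.1%. With 5% or 15% of initially negative patients detected instead of 10% (L = 0.5), it is 9.4–12.0% at 2 months and 6.3–7.1% at 6 months. A separate, smaller model (495 against 55, two groups, 300 runs, 0.3 acquisitions per year, 60-day spells, half local) agrees in direction: detection by month 6 of 4.5% against 8.0%, and 14% rejection with a simulation error of √(0.14 × 0.86 / 300) = 2 points.

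**4. At the plan's rates.** If 10% are detected over four visits, 1 − 0.9^(1/4) = 2.6% of initially negative patients are positive at month 6. With 85% placebo and 7%, 23% or 39% active, the three-group test on the common month-6 swab rejects in 100% of trials.

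Now put 85% in both arms, so that treatment does nothing. Carriers positive: 50 × 0.85 = 42.5. Initially negative positive: 450 × 0.026 = 11.7. Pooled proportion: 54.2 / 500 = 0.1084. Expected in carriers: 5.42, with variance 50 × 0.1084 × 0.8916 × 450/500 = 4.35. Chi-square is (42.5 − 5.42)² / 4.35 ≈ 316, against a 2-df critical value of 5.99. The omnibus test rejects without any arm difference.

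**5. Treated versus placebo.** 25 per arm, L = 0.5, 85% placebo positive, active 7% at day 28 and 39% by day 84 (the 28-day swab nearest day 90). The active hazard over days 28–84 is ln(0.93/0.61)/56 = 0.00753 per day. Continued for the 98 days to day 182, it gives 1 − 0.61·e^(−0.738) = 71% positive; half that hazard gives 58%. Power, unstratified / stratified by local status:

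| Active recolonization after day 84 | Active positive by day 182 | All visits on day 182 | Visits uniform over ±2 months |
|---|---|---|---|
| None | 39% | 93% / 98% | 83% / 87% |
| Half the hazard | 58% | 61% / 84% | 47% / 62% |
| Same hazard | 71% | 27% / 62% | 20% / 39% |

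A second run with the window gave 82/85, 45/58 and 22/39%. At 7% or 23% active, both tests exceed 99% with fixed visits. With no arm difference, both reject in 4–7% (fixed visits). Using local carriers alone gives 87% in the first row with fixed visits, so dropping non-local carriers is not the remedy.

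**6. Curves.** If placebo positivity is 85% at day 28, the placebo curve there is 1 − 0.85L. It reaches 0.50 at L = 0.588. The placebo median is thus 28 days or about six months, depending on where patients live.

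**The case against.** The strongest reply is that little depends on this. Question (1) uses the common visits, the primary endpoint rests on the 6-month follow-up visit, and no rule in section VII changes question (1) according to question (4). At spell lengths consistent with 85% persistence the error inflation is a point or two. All of that stands, and it is why the point is minor.

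A reader might infer more than the documents support:

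- **That nobody outside the local group can be found positive between days 28 and 168.** Not so. The ±2 month window lets a scheduled 6-month swab fall from about day 121, and infection visits add swabs for everyone. The window also shrinks the stratification gain in step 5.
- **That the randomized comparison is biased.** It is not. Randomization gives both arms the same expected mix of local and non-local carriers; the cost is power.
- **That power is really 20% or 27%.** Those cases take the active arm to 71% positive, beyond the planned 7–39%, and let only the active arm recolonize. If cleared placebo patients also recolonize, the fixed-visit figures are 61% unstratified and 94% stratified.
- **That any propensity finding would be an artefact.** At the plan's rates the difference appears on common visits too.

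One limit remains. Step 3 starts carriers negative, while step 5 counts persistent carriage at the first swab as the event. Because the plan gives no time origin, each step covers one reading of question (4).

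**Conclusion.** The point holds at reduced size; severity is minor. Question (4) pools unequal swab schedules in one log-rank and corrects for none of it, so the contrast of carriers with initially negative patients is partly a detection effect. With half of carriers local, that means about 5–7% false rejection for spells of 6 months or more and about 10% near 2 months. At the plan's rates it affects the apparent size and timing of the difference rather than the conclusion. The three-group test cannot answer the treatment half whatever the schedule. For treated versus placebo, the base-case cost is about 4 points of power with the visit window (83% against 87%), or 5 points if every visit falls on day 182. Larger losses need recolonization to continue after day 90, which the plan does not assume. These sizes rest on an assumed local share, spell length and spread of visits; step 3 was run only with fixed visit days.

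**What to change.** In section VII, question (4):

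1. Compare carriers with initially negative patients only on the 6, 12, 18 and 24 month swabs, treated as discrete visits. Interval censoring alone would handle timing, but not carriage that clears between looks.
2. Test treated versus placebo separately, from randomization, in all carriers, stratified by local status. Show monthly-swab curves and medians for local carriers only.

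Adding the local condition to footnote * of Appendix D is a clerical alignment with sections 5.1 and 6.3.

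The cost is a few sentences, with no added visits, swabs or patients. Timing in (1) becomes coarser, and local status must be recorded at randomization. Stratified power was equal or higher in every effect scenario run.
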